# 11.3.2 Assessment of Safety data

The number and percentage of subjects with solicited local and systemic reactions during the three days post-injection will be assessed. In addition, all adverse events (AE) and serious adverse events (SAEs), and new onset of chronic diseases (NOCDs) will be collected for the entire study period.

Specifically, the following safety parameters will be monitored and analyzed in terms of the number and proportion of participants reporting the following events will be assessed:

- Solicited local adverse events, including redness/erythema, swelling/induration and pain within 30 minutes of vaccination and over the 3-day period post vaccination (Day 0-3).
- Solicited systemic adverse events, including fever, fatigue/malaise, muscle aches, joint aches, chills, nausea, vomiting and headache within 30 minutes of vaccination and over the 3-day period post vaccination (Day 0-3).
- Unsolicited adverse events (AEs) occurring within 90 days post vaccination.
- Serious Adverse Events (SAE) occurring during the entire study period (Days 0-90).

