	
 
Solicited local adverse events, including redness/erythema, swelling/induration, pain and limitation of arm movement within 30 minutes of vaccination and over the 3-day period post vaccination (Day 0-3).
 
Solicited systemic adverse events, including fever fatigue/malaise muscle VEC aches, joint aches, chills, nausea and headache within 30 minutes of vaccination and over the 3-day period post vaccination (Day 0-3).
 
Unsolicited adverse events (AEs) occurring within 30 days post vaccination ROPICAL MEDICIN
 

• Serious Adverse Events (SAE) occurring during the entire study period (Days 0-90).

Occurrences of all events will be reported and summarized according to event severity, as "any local AE", or "any systemic AE", and by relationship to administration of study product, as deemed by a blinded study clinician. Percentage of participants experiencing each reaction or event, or at least one reaction or event will be calculated along with two-sided exact 95% CIs. The percentage of participants with solicited AE and SAEs will be compared between vaccine and comparator groups and a two-sided p-value of 0.05 will be considered statistically significant.

Inferential analyses

GMT ratios (GMT active comparator vaccine/GMT GPO Tri Fluvac) and difference of seroconversion rate (with two-sided 95% CI) related to the comparisons of interest will be computed. Acceptance value of GMT ratios at  $\leq 1.5$  and/or difference of seroconversion rate at  $\leq 10\%$  for the upper bound of the 95% CI will be considered for non-inferiority.

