# **Primary Safety Endpoints:**

The number and proportion of participants reporting the following events will be assessed:

- Solicited local adverse events, including redness / erythema, swelling / induration, pain, and limitation of arm movement within 30 minutes of vaccination and over the 3-day period post-vaccination (Days 0-3).
- Solicited systemic adverse events, including fever, fatigue/malaise, muscle aches, joint aches, chills, nausea, and headache within 30 minutes of vaccination and over the 3-day period post-vaccination (Day 0-3).
- Unsolicited Adverse Events (AEs) occurring within 90 days post-vaccination.
- Serious Adverse Events (SAE) occurring during the entire study period (Days 0-90).

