# 8.5 AE/SAE Reporting Period and Parameter

Safety events are reported from the time of study injection (Day 0) through completion of the study at Day 90. Specifically, solicited AEs to assess local and systemic reactogenicities will be collected at 30 minutes and then daily for 3 days thereafter. If a solicited AE started during the 3 days post-vaccination and continues beyond the 3 days it will continue to be reported as a solicited AE. Unsolicited AEs and SAEs will be reported from Day 0 through the end of the study at Day 90.

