# **11.4 Analysis of Safety Endpoints**

The safety profile of the GPO Tri Fluvac will be evaluated by the number and proportion of participants experiencing AEs by severity and relatedness to vaccination of the following five categories for all participants:

- A. Solicited local adverse events, including redness / erythema, swelling / induration, pain within 30 minutes of vaccination and over a 3-day period (Day 0-3) post-vaccination.
- B. Solicited systemic adverse events, including fever, fatigue, malaise, muscle aches, joint aches, chills, nausea, and headache within 30 minutes of vaccination and over a 3-day period (Days 0-3) post-vaccination.
- C. Unsolicited AEs occurring within 90 days post vaccination.
- D. SAEs occurring during the entire study period (Days 0-90).

Occurrences of all events will be reported and summarized according to event severity, as "any local AE", or "any systemic AE", and by relationship to administration of study product, as deemed by a blinded study clinician. Percentage of participants experiencing each reaction or event, or at least one reaction or event will be calculated along with two-sided exact 95% CIs. No statistical testing will be performed for unsolicited AEs; including SAEs. The percentage of participants with solicited AE and SAEs will be compared between vaccine and comparator groups and a two-sided p-value of 0.05 will be considered statistically significant.

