## II. Definitions of terms used in the Table:

Basic Self-care Functions Adult

Activities such as bathing, dressing, toileting, transfer/movement, continence, and feeding.

LLN Lower limit of normal

Medical Intervention Use of pharmacologic or biologic agent(s) for treatment of an AE

NA Not Applicable

Operative Intervention Surgical OR other invasive mechanical procedures.

ULN Upper limit of normal

Usual Social & Functional Activities Adult

Adaptive tasks and desirable activities, such as going to work, shopping, cooking, use of transportation, pursuing a hobby, etc.

PARAMETER	GRADE 1 MILD	GRADE 2 MODERATE	GRADE 3 SEVERE	GRADE 4 POTENTIALLY	
ESTIMATING SEVERITY GRADE					
SYSTEMIC					
Acute Allergic Reaction	Localized urticaria (wheals) with no medical intervention indicated	Localized urticaria with intervention indicated OR Mild angioedema with no intervention indicated	Generalized Urticaria OR Angioedema with intervention indicated OR Symptoms of mild bronchospasm	Acute anaphylaxis OR Life- threatening bronchospasm OR Laryngeal edema	
Chills	Symptoms causing no or minimal interference with usual social & functional activities	Symptoms causing greater than minimal interference with usual social & functional activities	Symptoms causing inability to perform usual social & functional activities	NA	
Fatigue or Malaise Report only one	Symptoms causing no or minimal interference with usual social & functional activities	Symptoms causing greater than minimal interference with usual social & functional activities	Symptoms causing inability to perform usual social & functional activities	Incapacitating symptoms of fatigue or malaise causing inability to perform basic self- care functions	
Fever (non-axillary	38.0 to < 38.6°C	$\geq$ 38.6 to < 39.3°C	$\geq$ 39.3 to < 40.0°C	≥40.0°C	
Fever (axillary)	37.7 – 38.1°C	38.2 – 38.8°C	38.9 - 40.0°C	>40.0°C	
Nausea	Transient (< 24 hours) or intermittent AND No or minimal interference with oral intake	Persistent nausea resulting in decreased oral intake for 24 to 48 hours	Persistent nausea resulting in minimal oral intake for > 48 hours OR Rehydration indicated (e.g., IV fluids)	Life-threatening consequences (e.g., hypotensive shock)	

HICS COMMITTEE Page 67 Aut 7.9 OF TROPICAL MEDICINE าริตยาลัยม MAHIDOL UNIVERSITY

APPROVED

US

R

ES
PARAMETER	GRADE 1 MILD	GRADE 2 MODERATE	GRADE 3 SEVERE	GRADE 4 POTENTIALL Y LIFE- THREATENIN

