	Tri fluvac (N = xx)	Comparator (N = xx)	Tri fluvac (N = xx)	Comparator (N = xx)	Tri fluvac (N = xx)	Comparator (N = xx)	Tri fluvac (N = xx)	Comparator (N = xx)
Min, Max								
P- value =								

	D	Day 0 Day 7		Day 21		Day 90		
	Tri fluvac (N = xx)	Comparator (N = xx)	Tri fluvac (N = xx)	Comparator (N = xx)	Tri fluvac (N = xx)	Comparator (N = xx)	Tri fluvac (N = xx)	Comparator (N = xx)
HEENT, n (%)								
Normal	xx(xx.xx)	xx(xx.xx)						
Abnormal	xx(xx.xx)	xx(xx.xx)						
P- value =	X.2	xxxx						
Lungs, n (%)								
Normal								
Abnormal								
P- value =								
Cardiovascular, n (%)								
Normal								
Abnormal								
P- value =								
Gastrointestinal, n (%)								
Normal								
Abnormal								
P- value =								
Musculoskeletal, n (%)								
Normal								
Abnormal								
P- value =								
Skin, n (%)								
Normal								
Abnormal								
P- value =								

TREF 3.4: Physical Examination by GPO Tri Fluvac and Active Comparator Group

	Day 0		D	Day 7		Day 21		Day 90	
	Tri Fluvac (N = xx)	Comparator (N = xx)	Tri Fluvac (N = xx)	Comparator (N = xx)	Tri Fluvac (N = xx)	Comparator (N = xx)	Tri Fluvac (N = xx)	Comparator (N = xx)	
Neurologic, n (%)	X	((
Normal	xx(xx.xx)	xx(xx.xx)							
Abnormal	xx(xx.xx)	xx(xx.xx)							
P- value =	X XXXX								

TREF 3.4: Physical Examination by GPO Tri Fluvac and Active Comparator Group (Continue)

TREF 3.5: Comparison of Maximum Grade of Any Local Reaction at Post Immunization by GPC
Tri fluvac and Active Comparator Group

Grade		Tri Fluvac (N = xx) n (%)	Comparator (N = xx) n (96)
Grada 0			
Grade 0		XX(XX.XX)	XX(XX.XX)
Grade 1		XX(XX.XX)	XX(XX.XX)
Grade 2		xx(xx.xx)	xx(xx.xx)
Grade 3		xx(xx.xx)	xx(xx.xx)
P- value =	X.XXXX		

Note: - Any local reaction on any day (by case)

- Erythema and Induration will be not included.

- Grading

- Grade 0 none
- Grade 1 mild
- Grade 2 moderate
- Grade 3 severe

TREF 3.6: Comparison of Local Reaction at Post Immunization each Follow up Time by GPO Tri Fluvac and Active Comparator Group

	30	min	D	Day 1	D	ay 2	Da	ny 3
Local Reaction	Tri Fluvac	Comparator						
	(N=xx)							
- Pain, n (%)	xx(xx.x)	xx(xx.xx)						
p-value =	X.:	xxxx						
- Limitation of arm movement, n (%)								
p-value =								
- Erythema (cm.)								
n								
Mean(SD)								
Median								
Min, Max								
p-value =								
- Swelling (cm.)								
n								
Mean(SD)								
Median								
Min, Max								
p-value =								
- Induration (cm.)								
n								
Mean(SD)								

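### The SAP's reaction tables do not follow the solicited-reaction lists that define the primary safety endpoint, so the any-local and any-systemic rates depend on which section is followed

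*Protocol*

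**What the plan says.** **The common list.** Protocol section 3 (Primary Safety Endpoints), the protocol summary, section 8.2 and the SAP synopsis agree on the solicited events. Local: redness, swelling/induration, pain and limitation of arm movement. Systemic: fever, fatigue/malaise as one item, muscle aches, joint aches, chills, nausea and headache. In section 3 the systemic list ends "chills, nausea, and headache within 30 minutes of vaccination", without vomiting.

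**The protocol's analysis sections.** Section 11.3.2 has "Solicited systemic adverse events, including fever, fatigue/malaise, muscle aches, joint aches, chills, nausea, vomiting and headache within 30 minutes of vaccination". Section 11.4 has "Solicited local adverse events, including redness / erythema, swelling / induration, pain within 30 minutes of vaccination". Both omit limitation of arm movement, and 11.4 also writes fatigue and malaise as two entries.

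**The SAP shells.** TREF 3.5 (maximum grade of any local reaction) and FREF 07 carry the note "Erythema and Induration will be not included". TREF 3.7 grades only pain and limitation of arm movement. TREF 3.9 offers no, one or two symptoms. TREF 3.11 to 3.13 have rows for headache, fatigue, malaise, chills, myalgia, arthralgia, nausea, vomiting and rash, and TREF 3.14 counts up to nine symptoms. Appendix A of the protocol heads the tiredness row "Fatigue or Malaise Report only one".

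**The unsolicited window.** The protocol summary has "Unsolicited adverse events (AEs) occurring within 30 days post vaccination" and section 3 has "Unsolicited Adverse Events (AEs) occurring within 90 days post-vaccination". Section 8.5 says "Unsolicited AEs and SAEs will be reported from Day 0 through the end of the study at Day 90". Sections 11.3.2 and 11.4 and the SAP synopsis also give 90 days.

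**How the events are used.** Both documents plan the percentage with each reaction and with at least one reaction, with exact 95% intervals. Both also plan a comparison of solicited events between arms at a two-sided 0.05 level.

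**The concern.** Solicited reactions are a primary safety endpoint, and the at-least-one-reaction percentages are its summary figures. A programmer working from the shells would produce an any-local rate that does not match the definition in the SAP's own synopsis. A programmer working from section 11.4 would produce a third version, with redness but without arm movement.

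The gap goes beyond the composite. In the summary tables, redness, swelling and induration appear only in TREF 3.6, as a count and a size in centimetres at each time point among those affected. No summary shell gives the proportion with redness or with swelling/induration over Days 0 to 3, which is what the endpoint text asks for. If the composition is still open when results are seen, the choice between versions is no longer blind.

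**Working it through.** The plan states no figure that depends on this point, so there is none to reproduce. The check sets the lists side by side.

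| Item | Section 3, 8.2, summary, SAP synopsis | 11.3.2 | 11.4 | SAP shells |
|---|---|---|---|---|
| Redness | yes | yes | yes | size in TREF 3.6; excluded from TREF 3.5 and FREF 07 |
| Swelling/induration | one item | one item | one item | sizes in TREF 3.6; induration excluded from TREF 3.5 and FREF 07, swelling not mentioned |
| Pain | yes | yes | yes | graded |
| Limitation of arm movement | yes | no | no | graded |
| Fever | yes | yes | yes | TREF 3.1 and 3.2 only |
| Fatigue/malaise | one item | one item | two | two |
| Muscle aches, joint aches, chills, nausea, headache | yes | yes | yes | yes |
| Vomiting | no | yes | no | yes |
| Rash | no | no | no | yes |

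**Local.** The common list has 4 items, 11.3.2 and 11.4 have 3, and TREF 3.7 and 3.9 have room for 2. A participant with redness alone is Grade 0 in TREF 3.5 and has no symptom in TREF 3.9, yet appears in TREF 3.6.

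**Systemic.** The common list has 7 items. The shells have 7 − 1 (fever) + 1 (fatigue and malaise split) + 2 (vomiting, rash) = 9, matching the maximum in TREF 3.14. Rash is in no protocol list of solicited events. Vomiting is listed for assessment only in sections 8.6 and 11.3.2, although Appendix A has grades for it.

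**Size, from the phase I/II results in protocol section 2.4 (200 vaccine recipients):**

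- *Swelling.* Pain was 32.5% and swelling 2.5% (0.025 × 200 = 5 people). If every swelling came with pain, the rate with either is 32.5%; if none did, it is 32.5 + 2.5 = 35.0%. Leaving swelling out therefore lowers any local reaction by 0 to 2.5 points, at most 0.025 × 630 ≈ 16 participants in the Tri Fluvac arm. The exact 95% interval for 5/200 is 0.82% to 5.74%.
- *Fever.* None was reported. The exact two-sided 95% upper limit for 0/200 is 1 − 0.025^(1/200) = 1.83%. Only fever with no other counted symptom would alter any systemic reaction, so the effect is probably below about 2 points.
- *Erythema, vomiting and rash.* The documents give no rate for this product, so no effect can be computed. Adding vomiting and rash can only raise the any-systemic rate; omitting fever can only lower it.

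**Unsolicited window.** One entry says 30 days. Section 3, section 8.5, 11.3.2, 11.4 and the SAP synopsis say 90. Collection runs to Day 90, so data exist for either.

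**The case against.** The strongest reply is that the endpoint is already settled. Section 8.2 names the specific events to be reported, section 3 and the SAP synopsis match it, and the shorter lists in 11.3.2 and 11.4 are introduced as inclusive, not exhaustive. Erythema and induration are measured in centimetres, which may explain their absence from a table of grades. Most single-item results remain available: TREF 3.2 for fever, TREF 3.6 for erythema, swelling and induration. This limits the consequence to composites and symptom counts. It does not remove the problem, because the exclusion note in TREF 3.5 is explicit, and Appendix A converts diameters to grades, so the unit of measurement is no bar.

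Four stronger readings are tempting, and the documents do not support them.

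- *That the SAP drops fever from the systemic endpoint.* The SAP synopsis lists it, and TREF 3.1 and 3.2 tabulate temperature grade, TREF 3.2 at 30 minutes and Days 1 to 3. Fever is missing only from TREF 3.11 to 3.14. TREF 3.10 names no components, so whether isolated fever counts there is undefined.
- *That one complaint of tiredness will be counted twice.* This happens only if sites ignore the one-term rule in Appendix A. The split is also not peculiar to the SAP, since section 11.4 makes it too.
- *That fever could move the composite by 7.6 points.* That rate comes from a published trial of another vaccine cited in section 2.4. Using it as a shift also assumes that no fever came with any other counted symptom. This product's own result is 0 of 200.
- *That two thirds of follow-up would be lost for unsolicited events.* That requires following one synopsis line against five other statements, including the SAP's.

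**Conclusion.** The point holds for the shells and for sections 11.3.2 and 11.4. As drawn, the any-local tables do not measure the endpoint in section 3 and the SAP synopsis, and the systemic tables use a different symptom set. The effect falls on composite rates, symptom counts and the missing Day 0 to 3 proportions for redness and swelling/induration.

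It is probably small: 0 to 2.5 points on any local reaction from swelling, and under about 2 points on any systemic reaction from fever. These figures assume that phase I/II rates carry over. The first also assumes that swelling is left out along with induration, which the TREF 3.5 note does not say but the shape of TREF 3.7 and 3.9 implies. The effect of erythema, the clearest exclusion, is unknown.

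No non-inferiority conclusion depends on any of this. The 30-day entry is a single inconsistency to be reconciled. The correction should be made, but the point does not threaten the trial's main result.

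**What to change.** Before unblinding:

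1. Build TREF 3.5, 3.7, 3.9, 3.10 and 3.14 from the list shared by section 3, section 8.2 and the SAP synopsis. Local: redness, swelling/induration, pain, limitation of arm movement. Systemic: fever, fatigue/malaise as one item, muscle aches, joint aches, chills, nausea, headache. Remove the exclusion note from TREF 3.5 and FREF 07.
2. Use Appendix A grades where they are defined, and add a Grade 4 row. TREF 3.5 and 3.10 stop at Grade 3, while Appendix A and TREF 3.2 go to Grade 4. Because Appendix A grades redness only from 2.5 cm, state how smaller redness is counted.
3. Add the Day 0 to 3 number and proportion, by arm, with redness and with swelling/induration.
4. State whether vomiting and rash are solicited events in the composite or are reported separately. Either is workable if said in advance.
5. Align 11.3.2 and 11.4 with the same list, including limitation of arm movement.
6. Reconcile the 30-day entry in the protocol summary with the 90 days in section 3, 8.5, 11.3.2, 11.4 and the SAP synopsis.

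The cost is wording and shell edits. The planned diary, temperature and measurement data already cover the common list, so no new collection or sample size change is needed.

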# 11.3.3 Exploratory Analysis:

-

# **11.4 Analysis of Safety Endpoints**

The safety profile of the GPO Tri Fluvac will be evaluated by the number and proportion of participants experiencing AEs by severity and relatedness to vaccination of the following five categories for all participants:

- A. Solicited local adverse events, including redness / erythema, swelling / induration, pain within 30 minutes of vaccination and over a 3-day period (Day 0-3) post-vaccination.
- B. Solicited systemic adverse events, including fever, fatigue, malaise, muscle aches, joint aches, chills, nausea, and headache within 30 minutes of vaccination and over a 3-day period (Days 0-3) post-vaccination.
- C. Unsolicited AEs occurring within 90 days post vaccination.
- D. SAEs occurring during the entire study period (Days 0-90).

Occurrences of all events will be reported and summarized according to event severity, as "any local AE", or "any systemic AE", and by relationship to administration of study product, as deemed by a blinded study clinician. Percentage of participants experiencing each reaction or event, or at least one reaction or event will be calculated along with two-sided exact 95% CIs. No statistical testing will be performed for unsolicited AEs; including SAEs. The percentage of participants with solicited AE and SAEs will be compared between vaccine and comparator groups and a two-sided p-value of 0.05 will be considered statistically significant.

# 11.5 Analysis of Immunogenicity Endpoints

Primary Endpoint:

The primary analyses of immune responses to the GPO Tri Fluvac 21 days post-injection will be performed based on According to Protocol (ATP) cohort by the following:

A. Number and percentage of participants with seroconversion against each of the the three waccine IVERSITY

215

antigens post-vaccination. Seroconversion is defined as a serum HI antibody titer meeting the following criteria:

- Pre-vaccination titer <1:10 and a post-vaccination titer measured on Day 21 of  $\ge1:40$ , or
- Pre-vaccination titer ≥1:10 and at least a four-fold increase in post-vaccination measured on Day 21.

B. Geometric mean titers of serum HI antibodies pre- (Day 0) and post-vaccination (Day 21) for each of the three vaccine antigens.

Titers below the lowest limit of quantitation (i.e., below the starting dilution of assay reported as "< 10") will be set to half that limit (i.e., 10/2 = 5). If a titer is reported as greater or equal to the upper limit of the assay, it will be set to that limit.

Secondary Immunogenicity Endpoints:

The secondary immunogenicity endpoints will be analyzed by the following:

- A. Number and percentage of participants with a HI antibody titer  $\geq 1:40$  (seroprotective level) to each of the three vaccine antigens measured on Day 21 and Day 90.
- B. Number and percentage of participants who develop at least a four-fold increase in HI antibody titers to each of the vaccine antigen post-vaccination measured on Day 21 and Day 90 segregated by pre-vaccination HI antibody titers (<1:10 or ≥1:10).
- C. Geometric mean fold rises (GMFRs) of serum HI antibodies (post-vaccination/ pre-vaccination) for each of the three vaccine antigens
- D. GMTs of serum HI antibodies pre- (Day 0) and post-vaccination (Day 21 and Day 90) for each of the three vaccine antigens by pre-vaccination HI antibody titers ( $<1:10 \text{ or } \ge 1:10$ ).
- E. GMFRs of serum HI antibodies (pre- and post-vaccination) for each of the three vaccine antigens segregated by pre-vaccination HI antibody titers (<1:10 or  $\ge1:10$ ).

The proportions of seroconversion responders, at Day 21 between groups (vaccines or comparator) will be examined and compared to determine the effect of an inactivated trivalent influenza vaccine. The antibody titers of each group will also be presented as GMT. The 95% CI and *p*-value will be calculated and presented. Multivariate analysis will be performed as needed to explore potential confounders.

# **11.6 DATA HANDLING AND RECORD KEEPING**

The site PIs are responsible for ensuring the accuracy, completeness, and timeliness of the data reported. Data collection is the responsibility of the clinical trial staff at the study site under the supervision of the site PIs or designee. Data collection must be completed as soon as possible to allow for timely review of safety information. The BIOPHICS will be responsible for data management activities, including quality review, analysis, and reporting of the study data according to SOPs.

ETHICS COMMITTEE FACULTY OF TROPICAL MEDICINE MAHIDOL UNIVERSITY

